12. STATISTICAL METHODS AND SAMPLE SIZE DETERMINATION

12.1 Description of analysis sets

12.1.1 General principles

The analysis of data will be based on different subsets according to the purpose of analysis ie, for safety and PK, respectively.

12.1.2 Safety analysis set

All volunteers who receive at least 1 dose of the AZD6244 and for whom any postdose safety data are available will be included in the safety population.

12.1.3 Pharmacokinetic analysis set

12.1.3.1 Interim analysis

An interim PK analysis will be conducted following Treatment Period 3. All volunteers from each dose that receive active drug will be included in the analysis dataset. The same rules of analysis as described in Section 6.4 will be followed.

General conditions for the interim PK analysis:

- Single analyte of AZD6244 in plasma
- Analysis for estimation of PK parameters using nominal times of sample collections so no merging of bioanalytical data with the database is needed
- Outcome variables to be analyzed are limited to $AUC_{(0-t)}$, C_{max} , and t_{max} , no curve stripping on individual concentration versus time plots will be performed
- Prior to the analysis or receipt of the bioanalytical data, a safety team member or study center staff member will need to provide information of volunteers who had AEs reported or other conditions that would affect the delivery of study drug (ie, primarily emesis post drug administration) during the study in order to evaluate the volunteers for exclusion within the PK analysis
- Informal table and mean figures from the analysis software o reduce involvement of programming team members
- Brief summary by descriptive statistical table, no inferential statistical

Internal review of analysis and outputs but no formal quality control or quality audits

12.1.3.2 Final analysis

The PK analysis set will be a subset of the safety analysis set and will include all healthy volunteers who receive at least 1 dose of IP (AZD6244) without important CSP deviations or violations thought to significantly affect the PK (eg, vomiting within 3 to 4 hours after IP administration on any day in the study; volunteer vomited at or before 2 times median t_{max} ; wrong dose administered; prohibited concomitant medication; etc). A strategy for dealing with data affected by CSP violations, deviations, and events will be agreed upon by the pharmacokineticist and statistician prior to PD analysis. Volunteers will be analyzed according to the treatment they actually received.

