6.5 Pharmacodynamics (not applicable)

6.6 Pharmacogenetics

All volunteers enrolled in the study will have the option to provide a blood sample for pharmacogenetic analysis. Volunteers will not be excluded from participating in the study if they decline participation in the genetic analysis. Blood samples for these analyses will be taken only after the volunteer has signed a separate genetic informed consent for sample collection. The analyses and results from these optional studies will be handled and reported separately from the main study.

Collection of pharmacogenetic samples

The blood sample for genetic research will be obtained from the volunteers on Day 1 of Period 1. Although genotype is a stable parameter, early sample collection is preferred to

avoid introducing bias through excluding volunteers who may withdraw due to an AE, such volunteers would be important to include in any genetic analysis. If for any reason the sample is not drawn on Day 1 of Period 1, it may be taken at any visit until the last study visit. Only 1 sample should be collected per volunteer for genetics during the study. Samples will be collected, labeled, stored, and shipped as detailed in the Laboratory Manual.

For blood volume see Section 7.1.

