12.2.2 Pharmacokinetic analyses

Pharmacokinetic blood sample collection times as well as derived sampling time deviations will be listed. Plasma concentration-time data (for AZD6244, *N*-desmethyl AZD6244 and AZD6244 amide) will be listed and summarized by treatment.

Data from volunteers excluded from the PK analysis population will be included in the data listings, but not in the summaries.

Pharmacokinetic variables will be summarized by treatment using appropriate descriptive statistics (eg, *n*, geometric mean, coefficient of variation [CV], minimum, median, and maximum) for all variables except t_{max} which will use *n*, arithmetic mean, standard deviation (SD), minimum, median, and maximum. The geometric mean is calculated as the exponential of the arithmetic mean calculated from data on a log scale.

The CV is calculated as:

$$100 \cdot \sqrt{(\exp(s^2) - 1)}$$

where s is the SD of the data on a log scale.

For descriptive statistics, concentrations below lower limit of quantitation (LLOQ) values will be handled as follows:

- At a time point where less than or equal to 50% of the values are below the LLOQ (BLQ), all BLQ values will be set to LLOQ, and all descriptive statistics will be calculated
- At a time point where more than half of the values are BLQ, the mean, SD, geometric mean and CV% will be set to 'not determined' (ND). The maximum value will be reported from the individual data, and the minimum and median will be set to BLQ
- If all values are BLQ at a time point, no descriptive statistics will be calculated for that time point. Not applicable (NA) will be written in the field for SD and CV%, and BLQ will be written in fields for mean, geometric mean, min, median, and max
- The number of BLQ values (n below LLOQ) will be reported for each time point.

Figures of arithmetic mean (\pm SD) plasma concentration-time data (for AZD6244, *N*-desmethyl AZD6244, and AZD6244 amide) up to 36 hours after the dose of each treatment period will be presented by treatment on both the linear and semi-logarithmic scales. Individual volunteer concentration-time data will be plotted on linear and semi-logarithmic scales.

Geometric mean and individual AUC and C_{\max} values will be presented by treatment. Graphical presentations of other PK data may be added at the discretion of the pharmacokineticist.

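### As worded, the PK analysis set can drop a volunteer's unaffected A and B profiles for an event at another dose, and nothing requires exclusions to be settled before the interim PK summary of Periods 1-3

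*Protocol*

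**What the plan says.** **Unit of exclusion.** Section 12.1.3.2 admits volunteers who receive at least one dose "without important CSP deviations or violations thought to significantly affect the PK". Its examples include "vomiting within 3 to 4 hours after IP administration on any day in the study; volunteer vomited at or before 2 times median" t_max, with wrong dose and prohibited medication also listed. Section 12.2.2 adds: "Data from volunteers excluded from the PK analysis population will be included in the data listings, but not in the summaries". Both sections speak of volunteers. Section 11.2 works differently: if the predose concentration exceeds 5% of C_max, parameters for that profile alone are not reported.

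**Data used.** Under Section 12.2.2, B versus A is estimated from the first three periods only. Every volunteer receives four doses: A, C and B once each in Periods 1-3, and B again in Period 4 (Section 5.2, Table 5).

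**Timing.** The strategy for affected data is to be "agreed upon by the pharmacokineticist and statistician prior to PD analysis". Section 6.5 is headed "Pharmacodynamics (not applicable". Section 1.3.3 calls the digital ECGs pharmacodynamic assessments, but Section 12 describes no PD analysis. Section 12.1.3.1 states: "An interim PK analysis will be conducted following Treatment Period 3". That interim is descriptive, covering AUC(0-t), C_max and t_max. Before the analysis or the arrival of bioanalytical data, staff must report volunteers with emesis or similar events so that they can be considered for exclusion.

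**The concern.** An event at C or in Period 4 says nothing about whether that volunteer's A profile and first B profile are valid. Removing them costs evaluable A-B pairs for no gain in validity. The trial recruits 30 to secure 24, so the whole reserve is six.

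The second issue is when exclusions are decided. The study is open-label, and by the end of Period 3 all data for the primary comparison exist. Section 12.2.1 presents treatments separately by default, so the interim table and mean figures would show A beside B. If the strategy is agreed only before the final analysis, decisions about who enters the primary comparison can follow that look.

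The two emesis examples add room for judgement. One limit is itself a range. The other depends on a median t_max and does not say whether it is pooled or taken per treatment.

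**Working it through.** **1. The plan's own figure.** Section 12.3 gives a within-volunteer variability of 0.04 for AUC, 24 evaluable volunteers, limits of 80.00% to 125.00%, a 90% CI and 95% power. Read 0.04 as a log-scale variance and take a true ratio of 1:

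- SE = √(2 × 0.04 / 24) = 0.0577; ln 1.25 = 0.2231; t(0.95, 44 df) = 1.680.
- Approximate power = 2Φ(0.2231/0.0577 − 1.680) − 1 = 2Φ(2.185) − 1 ≈ 0.97.
- Integrating over the residual variance gives 0.969 (44 df), or 0.964 with 22 df.

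The stated 95% is reproduced; the sample size is not in question.

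**2. Expected loss.** Let q be the probability of a disqualifying event per dose, assumed independent across doses.

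- Volunteer-level rule: lost if any of four doses is affected, 1 − (1 − q)⁴.
- Profile-level rule, for B versus A: lost only if A or the first B is affected, 1 − (1 − q)².

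The only rate in the protocol is Table 1 (Section 1.3.2): vomiting in 1 of 65 cancer patients within 24 hours of a 75-mg dose. The higher rates below are assumptions. Power is averaged over a binomial number of losses from 24.

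| q | Lost, volunteer rule | Lost, profile rule | Of 30 | Power, volunteer rule | Power, profile rule |
|---|---|---|---|---|---|
| 1/65 | 6.0% | 3.1% | 1.8 vs 0.9 | 0.957 | 0.964 |
| 3% | 11.5% | 5.9% | 3.4 vs 1.8 | 0.943 | 0.958 |
| 5% | 18.5% | 9.8% | 5.6 vs 2.9 | 0.919 | 0.948 |
| 10% | 34.4% | 19.0% | 10.3 vs 5.7 | 0.823 | 0.917 |

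With 1/65 rounded to 1.5%, the first row reads 5.9% and 3.0%. Across the table, 45% to 49% of the volunteer-level losses come from C or Period 4 alone. This share follows from counting two of four doses as irrelevant to B versus A. Starting from 24 is pessimistic, since 30 are recruited.

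**3. The two emesis examples.** Twice the median t_max falls within 3 to 4 hours if the median is 1.5 to 2 hours. A median of 1 hour gives 2 hours; 2.5 hours gives 5 hours. The protocol states no t_max, so a numerical conflict is possible but cannot be shown. What can be shown is a gap: whether vomiting at 3.5 hours disqualifies is not settled by the first example, and is settled by the second only if twice the median reaches 3.5 hours.

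**4. Timing, set side by side.** Section 12.1.3.1 puts emesis information ahead of the concentrations, but as a condition of the interim analysis. It takes its analysis rules from Section 6.4, which covers sample collection and assay and contains no exclusion rule. Section 12.1.3.2, which governs the final set, refers neither to the interim nor to the receipt of concentrations. If PD is read as PK, the deadline may still fall after the interim.

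**The case against.** The strongest reply is that whole-volunteer exclusion is one reading and not a settled rule. The inclusion phrase can be parsed as needing at least one clean dose. The examples are introduced as examples. The strategy clause concerns affected data, and it would have little to do if every affected volunteer simply left the set. A Period 4 event can hardly be thought to affect the PK of an earlier profile. Section 12.2.1 reduces the sample endpoint by endpoint, and the detail may sit in the SAP. This stands far enough that valid profiles can be dropped, not that they will be. It does not remove the inconsistency, because the any-day wording and Section 12.2.2 point to the volunteer while Section 11.2 points to the profile.

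A reader might infer that the two emesis windows contradict each other. The documents do not support that: they are separate items in an open list, and without a t_max no conflict can be shown.

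A reader might also infer that exclusions from the primary comparison will be made after the results are known. That too goes beyond the text. Section 12.1.3.1 puts the emesis information on record before concentrations arrive for the interim, AE start and stop times are recorded (Section 6.3.3), and the interim carries no inference. What remains is narrower: the information is collected early, but no rule is fixed then and the final set is not bound by it.

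**Conclusion.** The concern holds in limited form. As worded, an event at C or in Period 4 can remove unaffected A and B profiles from a comparison that uses Periods 1-3 only, which is inconsistent with the profile-level rule in Section 11.2. The deadline for the handling strategy names an analysis that the protocol does not describe. Even corrected to PK, it would not have to precede the interim summary.

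The size is small at the protocol's own rate: about 0.9 additional volunteers of 30 and 0.7 points of power, with power still above 95%. That rate comes from cancer patients over 24 hours and is only an illustration for healthy volunteers; independence across doses is also assumed. Rates of about 5% or more, at which power starting from 24 falls visibly, have no support in the document. No stated figure is wrong. Severity is minor to moderate. The better reason to act is that membership of the primary analysis set should be governed by rules written before the data are seen.

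**What to change.** - **Unit.** In Sections 12.1.3.2 and 12.2.2, state that only the affected treatment-period profile is excluded and that the volunteer's other profiles remain, in line with Section 11.2.
- **Emesis.** Reconcile the two examples into one analysis criterion chosen in advance. A fixed window should have a single limit. If the criterion uses median t_max, say whose median. The rule can then be written beforehand, although the affected profiles cannot be identified until concentrations are known.
- **Timing.** Replace the reference to PD analysis with a requirement that the exclusion rules be documented before the bioanalytical data for Periods 1-3 are received, and before the Period 4 data for the final analysis. This extends the timing of Section 12.1.3.1 to the final set.

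The cost is wording and one sign-off brought forward. No sample, visit or sample-size change is needed. It should be done before the interim, because a rule written afterwards cannot be shown to be independent of the results.

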12.2 Methods of statistical analyses

12.2.1 General principles

The statistical analyses will be performed by

Standard Operating Procedures and Work Instructions will be used as the default methodology if not otherwise specified.

Data from each treatment will be presented separately unless stated otherwise.

Missing data will result in a reduced sample size for that endpoint. No action will be taken to handle missing data.

A healthy volunteer who withdraws prior to the last planned observation in a treatment period will be included in the analyses up to the time of discontinuation.

All derived variables/parameters will be rounded for reporting purposes in the summary tables and volunteer listings, as per SOPs.

12.2.2 Pharmacokinetic analyses

Pharmacokinetic blood sample collection times as well as derived sampling time deviations will be listed. Plasma concentration-time data (for AZD6244, *N*-desmethyl AZD6244 and AZD6244 amide) will be listed and summarized by treatment.

Data from volunteers excluded from the PK analysis population will be included in the data listings, but not in the summaries.

Pharmacokinetic variables will be summarized by treatment using appropriate descriptive statistics (eg, *n*, geometric mean, coefficient of variation [CV], minimum, median, and maximum) for all variables except t_{max} which will use *n*, arithmetic mean, standard deviation (SD), minimum, median, and maximum. The geometric mean is calculated as the exponential of the arithmetic mean calculated from data on a log scale.

The CV is calculated as:

$$100 \cdot \sqrt{(\exp(s^2) - 1)}$$

where s is the SD of the data on a log scale.

For descriptive statistics, concentrations below lower limit of quantitation (LLOQ) values will be handled as follows:

- At a time point where less than or equal to 50% of the values are below the LLOQ (BLQ), all BLQ values will be set to LLOQ, and all descriptive statistics will be calculated
- At a time point where more than half of the values are BLQ, the mean, SD, geometric mean and CV% will be set to 'not determined' (ND). The maximum value will be reported from the individual data, and the minimum and median will be set to BLQ
- If all values are BLQ at a time point, no descriptive statistics will be calculated for that time point. Not applicable (NA) will be written in the field for SD and CV%, and BLQ will be written in fields for mean, geometric mean, min, median, and max
- The number of BLQ values (n below LLOQ) will be reported for each time point.

Figures of arithmetic mean (\pm SD) plasma concentration-time data (for AZD6244, *N*-desmethyl AZD6244, and AZD6244 amide) up to 36 hours after the dose of each treatment period will be presented by treatment on both the linear and semi-logarithmic scales. Individual volunteer concentration-time data will be plotted on linear and semi-logarithmic scales.

Geometric mean and individual AUC and C_{\max} values will be presented by treatment. Graphical presentations of other PK data may be added at the discretion of the pharmacokineticist.

Primary PK parameters are AUC and C_{\max} of AZD6244. If AUC is not reportable in more than 60% of the 30 enrolled volunteers (ie, 18 reportable AUCs) then $AUC_{(0-t)}$ will be used in the inferential analysis.

Utilizing data from the first three treatment periods only, the relative bioavailability between treatments will be assessed between test (Treatment B) and reference (Treatments A) treatments. Analyses will be performed using a linear mixed-effect analysis of variance model using the logarithm of AUC and C_{\max} as the response variables, sequence, period, and treatment as fixed effects, and volunteer nested within sequence as a random effect. Transformed back from the logarithmic scale, geometric least-squares means together with confidence intervals (CIs) (2-sided 95%) for AUC and C_{\max} will be estimated and presented.

Also, ratios of geometric least squares means together with CI (2-sided 90%) will be estimated and presented.

Using a similar model as above, comparisons will be made for dose-normalized AUC and C_{\max} between test (Treatment B) and reference (Treatments C) treatment. AUC and C_{\max} will be dose-normalized prior to the ln-transformation.

Comparisons include:

- Treatment B versus A
- Treatment B versus C

Using treatment B data only, estimates of between and within-volunteer variability's will be obtained by employing a linear mixed-effect analysis of variance model using the logarithm of AUC and C_{\max} as the response variables and treatment as fixed effect. Volunteer nested within sequence will be a random effect. Treatment will be re-coded as B1 and B2, where B1 will correspond to Treatment B given in the first 3 periods and B2 will correspond to Treatment B given in Period 4. Estimates for the between and within-volunteer variability's will be present together with the associated 90% CIs.

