The oral solution proposed for use in this study has not previously been administered to humans in a clinical study. The dose for use in study D1532C00066 was selected based upon preclinical experience of the solution performance in both dog and monkey and the bioavailability observed. The relative bioavailability of the capsule formulation compared to the Phase I AZD6244 free base in Captisol[®] suspension (“mix and drink”) was comparable in preclinical studies in dog and in a clinical study in patients (D1532C00005). Therefore the relative bioavailability of the oral solution to the capsule in dog was considered to be predictive of the expected performance in human and this was used to derive a suitable dose. This preclinical relative bioavailability predicted a potential for up to a 2-fold difference in exposure (both C_{max} and AUC), and this also took into account that the oral solution is not dissolution rate limited and a more rapid and complete absorption is possible, resulting in a higher C_{max} . Therefore, in order to minimize the risk of exceeding the mean AUC and C_{max} observed with a 75-mg dose of the AZD6244 capsule formulation, a solution dose of 35 mg (approximately half that of the capsule) was recommended.

For Dosing Period 1, 2 volunteers will receive AZD6244 doses at least 2 days before the remainder of the volunteers.

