11.2 Calculation or derivation of pharmacokinetic variables

The PK analyses of the plasma concentration of AZD6244 amide will be performed. Pharmacokinetic analyses will be conducted according to the following procedures (SOPs) for PK analyses if not otherwise specified.

Pharmacokinetic parameters in plasma will be derived using noncompartmental methods with

Actual elapsed time from dosing will be used for final plasma PK parameter calculations. Pharmacokinetic parameter units will be consistent with the plasma concentration units specified in the bioanalytical data. No conversion of units will be made.

If data permits and unless otherwise stated, the following PK parameters will be determined for AZD6244, *N*-desmethyl AZD6244, and AZD6244 amide, following single-dose administration:

AUC	Area under the plasma concentration-time curve from zero to infinity (AUC, ng*h/mL), calculated by linear up/log down trapezoidal summation
-----	---------------------------------------------------------------------------------------------------------------------------------------------

$AUC_{(0-t)}$	Area under the plasma concentration-time curve from zero to the time of the last quantifiable concentration [$AUC_{(0-t)}$, ng*h/mL], calculated by linear up/log down trapezoidal summation
$AUC_{(0-12)}$	Area under the plasma concentration-time curve from zero to the time of 12 hours [$AUC_{(0-12)}$, ng*h/mL], calculated by linear up/log down trapezoidal summation
C_{max}	Maximum plasma concentration (C_{max} , ng/mL), obtained directly from the observed concentration versus time data
t_{max}	Time to C_{max} (t_{max} , h)
CL/F	Apparent oral plasma clearance (CL/F, L/h, AZD6244 only)
V_{ss}/F	Apparent volume at distribution equilibrium, $MRT*CL/F$ (V_{ss}/F , L, AZD6244 only)
V_z/F	Apparent volume of distribution (V_z/F , L, AZD6244 only)
$t_{1/2}$	Terminal half-life ($t_{1/2}$, h)
λ_z	Terminal rate constant (λ_z , 1/h).

Metabolite to parent drug ratios will be calculated for the primary PK parameters AUC and C_{max} .

The following PK parameters will be calculated for diagnostic purposes and listed, but will not be summarized:

- The time interval (h) of the log-linear regression to determine $t_{1/2}$ ($t_{1/2}$, interval)
- Number of data points ($t_{1/2}$, N) included in the log-linear regression analysis used to determine λ_z . A minimum of 3 data points will be used for λ_z determination

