- Coefficient of determination for calculation of λ_z (Rsqr). The λ_z and related parameters will be reported only if Rsqr is 0.800 or more
- Percentage of AUC obtained by extrapolation (%AUC_{ex}); if the extrapolated area (%AUC_{ex}) is greater than 20% then AUC for that specific profile will not be reported

Pharmacokinetic parameters shall be computed and reported if the anomalous predose concentration value is not greater than 5% of the maximum observed concentration (C_{max}) in the profile. If the anomalous predose concentration value is greater than 5% of the maximum observed concentration (C_{max}) in the profile, PK parameters for the profile shall not be reported. If an anomalous concentration value is observed at the terminal phase and is judged as physiologically unreasonable, it will be excluded from computing parameter estimates.

Additional PK parameters may be calculated if deemed appropriate.

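### If the AUC(0-t) fallback is triggered, the dose-normalised B versus C comparison can rest on curves that stop at different times, which can bias the ratio

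*Protocol*

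**What the plan says.** The relevant text is all in the protocol.

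- **Fallback (Section 12.2.2).** The condition is "If AUC is not reportable in more than 60% of the 30 enrolled volunteers (ie, 18 reportable AUCs"; AUC(0-t) then "will be used in the inferential analysis". The section lists two inferential comparisons, B versus A and B versus C, and the fallback excludes neither.
- **B versus C (Section 12.2.2).** "Using a similar model as above, comparisons will be made for dose-normalized AUC" and Cmax, with dose normalisation done before the log transformation. The doses are 75 mg for B and 35 mg for C (Section 5.5.2).
- **End point of AUC(0-t) (Section 11.2).** The area runs "from zero to the time of the last quantifiable concentration". No common end time is required across treatments.
- **When AUC is withheld (Section 11.2).** If the extrapolated share "is greater than 20% then AUC for that specific profile will not be reported". The terminal rate constant must also reach an Rsq of 0.800.
- **Why 35 mg (Section 3.3).** "This preclinical relative bioavailability predicted a potential for up to a 2-fold difference in exposure", for both Cmax and AUC.
- **Sampling (Tables 2 and 3).** The grid is the same for every treatment, and the last three samples are at 12, 24 and 36 h.

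AUC(0-12), an area over a fixed interval, is already a planned parameter but is not named as a fallback.

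**The concern.** Dose normalisation makes two full AUCs comparable under linear kinetics. It does not do so for truncated ones. Where the assay limit sets the last point, each curve loses roughly the same absolute area beyond it, and that is a larger share of whichever curve is smaller. On a grid as sparse as 12, 24 and 36 h, the smaller curve may also lose a whole sample that the larger one keeps.

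Relative bioavailability of the blue capsule against the solution is a stated secondary objective (Section 2.2). If the fallback is used as written, that ratio could partly reflect where the assay stopped rather than how much drug was absorbed.

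**Working it through.** **1. The plan's own figures.** 0.6 × 30 = 18, as stated. (Read literally, more than 60% not reportable would leave 11 or fewer; the present point holds under either reading.) Section 12.3 gives 95% power for AUC with 24 volunteers and within-volunteer variability 0.04. Taking 0.04 as a log-scale variance, SE = sqrt(2 × 0.04/24) = 0.058. Two one-sided tests then give 96.4% to 96.9% power at a true ratio of 1.00 and 94.1% to 94.7% at 1.03 (22 or 44 degrees of freedom), so the stated figure reproduces. The 90% CI half-width is about 0.10 on the log scale.

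**2. Truncation at a common concentration.** Let R be the solution's bioavailability per mg relative to the capsule. Then r = AUC_C/AUC_B = (35/75) × R. If both curves stop at the same concentration with the same terminal rate, both lose the same area. If that area is a share g of the solution AUC, it is g × r of the capsule AUC. The factor on the dose-normalised B/C ratio is

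K = (1 − g × r)/(1 − g).

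| R | r | K, g = 20% | K, g = 30% |
|---|---|---|---|
| 1.0 | 0.467 | 1.133 | 1.229 |
| 1.5 | 0.700 | 1.075 | 1.129 |
| 2.0 | 0.933 | 1.017 | 1.029 |
| 2.14 | 1.000 | 1.000 | 1.000 |
| 2.5 | 1.167 | 0.958 | 0.929 |

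The sign changes at R = 75/35 = 2.14. The direction therefore depends on which treatment has the lower absolute exposure, not on the mg doses alone.

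**3. The actual sampling grid.** A one-compartment model was run on the protocol's sampling times with linear-up/log-down areas. Assumed, because the protocol gives none of these: absorption rates of 1.5/h (capsule) and 3/h (solution), half-lives of 5 to 18 h, and LLOQ from 0.1% to 20% of capsule Cmax. Here K = (1 − unobserved share of B)/(1 − unobserved share of C). Examples at R = 1:

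| Half-life | LLOQ, % of capsule Cmax | Last time B, C | Unobserved B, C | K |
|---|---|---|---|---|
| 18 h | 1% | 36, 36 h | 25.7%, 25.4% | 0.996 |
| 8 h | 5% | 36, 24 h | 4.7%, 12.9% | 1.095 |
| 5 h | 5% | 24, 12 h | 4.0%, 20.0% | 1.20 |
| 8 h | 10% | 24, 12 h | 13.3%, 36.6% | 1.367 |
| 12 h | 20% | 24, 12 h | 26.1%, 51.2% | 1.514 |

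In a single volunteer the effect is close to all-or-nothing. K is 0.98 to 1.00 when both curves end at the same sample. It is clearly above 1 when the solution ends one sample earlier: about 1.14 or more if at least one curve has over 20% unobserved, and less where the tails are small (1.095 in the second row). Across wider grids of assumed half-life and LLOQ, restricted to scenarios with over 20% unobserved, the end samples differed in roughly 35% to 40% of scenarios at R = 1, 16% to 20% at R = 1.5 and 3% to 5% at R = 2. These shares depend on the values assumed and are not probabilities.

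**4. Same end time.** In the fourth row, cutting both curves at 12 h leaves 37.7% and 36.6% unobserved. K becomes 0.623/0.634 = 0.983 instead of 1.367.

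**The case against.** The strongest reply is that the problem needs several conditions at once: the fallback must fire, curves must drop below the LLOQ before 36 h, and the two treatments must end at different samples. The trigger does not imply the rest. With a mono-exponential decline, 20% is unobserved at 36 h once the half-life exceeds 36 × ln 2/(−ln 0.20) = 15.5 h. Both curves can then still be quantifiable at 36 h and are cut at the same time. A poor Rsq can also make AUC unreportable without a large tail. In addition, the 35 mg dose was chosen to bring the exposures close together; at the 2-fold advantage the bias is only 2% to 3% in the common-concentration calculation. B versus C is a secondary estimate with no acceptance limits or power statement of its own. A statistical analysis plan could also refine the parameter choice, and Section 11.2 allows extra parameters.

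Most of this stands, and it keeps the severity low. It does not remove the point. The protocol states the fallback as a rule and applies it to this comparison. Two-fold is the top of the predicted range, derived from animal data for a solution not previously given to humans, and the bias grows below it.

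Three stronger readings are tempting but not supported:

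- **That the bias certainly favours the capsule.** It does so only below a 2.14-fold advantage and only when the curves end differently.
- **That the fallback fires exactly when truncation is unequal.** The long half-life case above shows otherwise.
- **That the error is 40% or more.** Putting the 20% threshold on the capsule curve at R = 1 gives 0.80/(1 − 0.20/0.467) = 1.40, and a 30% capsule tail gives 1.96. These imply that 43% and 64% of the solution AUC is unobserved, which nothing in the protocol indicates.

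**Conclusion.** The point holds as a conditional weakness of low severity. As written, the fallback can compare areas cut at different times in the one comparison where the doses differ, and dose normalisation does not repair that.

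Assuming linear kinetics, a common terminal rate and LLOQ-limited curves, with 20% of the solution AUC cut off, the B/C ratio is overstated by about 13%, 7.5% and 2% at R = 1, 1.5 and 2. On the log scale 1.133 is 0.125, which exceeds the planned 90% CI half-width of about 0.10 if the 0.04 variance also applies to B versus C and all volunteers are affected alike; 1.075 is 0.072, which does not. If only some volunteers have unequal ends, the average bias is diluted: one third at 1.14 would give exp(0.131/3) = 1.045.

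Without an LLOQ or half-life, the protocol does not allow the size or even the occurrence to be fixed. The equal-dose primary comparison, B versus A, is not touched by this problem.

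**What to change.** In Section 12.2.2, keep AUC(0-t) as the fallback for B versus A. For B versus C, state one rule: if the fallback is triggered, analyse the dose-normalised area up to the earlier of the two last quantifiable times in the same volunteer, using the B and C profiles that enter that comparison. Report the already derived AUC(0-12), dose-normalised, as supportive only, so that no choice between measures is left open.

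The cost is one sentence and a small extra derivation from samples already planned. The downside is that the common interval covers less of the curve and is therefore somewhat more sensitive to absorption rate. In the model this shifts the ratio by up to about 2% toward the solution in typical cases (factor 0.98 to 1.00). The shift is a few percent if the capsule absorbs slowly, and more if the common end time is very early.
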